4.3 Target Sample Size

This clinical trial aims at enrollment of 30 subjects in total. At least 2 subjects for each approach, and at least 1 subject for each size should be enrolled, so that the safety and efficacy for the TF, TA, and TAO approaches and all THV sizes (20, 23, 26, and 29 mm) could be evaluated. Enrollment will be closed when the number of patients enrolled in the study reaches the target sample size even when the above-mentioned number of patients are not ensured. Additional subjects will not be included for discontinued subjects.

Table 4-7: Target Sample Size

Target sample size by approach	Target Sample Size
Transfemoral approach	≥ 2 subjects
Transapical approach	≥ 2 subjects
Transaortic approach	≥ 2 subjects
Target sample size by valve size	
20 mm	≥ 1 subject
23 mm	≥ 1 subject
26 mm	≥ 1 subject
29 mm	≥ 1 subject

A total of 30 subjects

<Rationales for the setting>

The sample size for this clinical trial was calculated based on the number of subjects required to verify noninferiority of the study treatment to the standard therapy by comparing the primary endpoint of all-cause mortality at 1 year post-procedure with the PG. Based on the results of the advanced medical care given in Osaka University Hospital, PREVAIL-JAPAN study, and SAPIEN XT post-marketing surveillance,

- 46 -

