7.3 Post-procedural Follow-up Observation

All subjects for whom the THV was implanted and maintained at the time point when the subject left the operation room should undergo the 5-year post-procedural follow-up observation specified in the protocol. For study discontinuation subjects without implantation of the investigational valve for the reasons that the procedure was switched to surgery, or already approved TAVI bioprosthetic valve was implanted, participation in this trial should be discontinued at the time point, and follow-up observation will not be required thereafter.

For the test/observation items and timing in the post-procedural follow-up observation, see Section 10.

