14 SUBJECT TREATMENT DISCONTINUATION

14.1 Subject Treatment Discontinuation

Enrolled subjects will continuously participate in the clinical trial until all follow-up observations specified in the protocol are completed. However, the following subjects should discontinue the trial.

- A subject or the legal representative requests discontinuation of the participation in the clinical trial.
- The principal investigator or subinvestigators judges that continued trial will be a disadvantage for subject's health condition.
- The study procedure has not been started.
- When the subject is exiting the operation room, the investigational valve has not been implanted.
- The investigational valve was removed.
- The subject died.
- Continued participation in the clinical trial was deemed difficult.
- The sponsor requests (continued trial was determined to be a disadvantage in the subjects).

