14.2 Subject Treatment Discontinuation Procedure

When a subject discontinues participation in the clinical trial, the following procedure should be used.

- The investigators should enter the date of discontinuation, reason for discontinuation, AE incidence status, and drug therapy status in the eCRFs. To ensure the safety of discontinued subjects, all possible measures should be taken, appropriate treatment should be given, and also for the safety after discontinuation, perform follow-up investigation as much as possible.
- If a subject discontinued the trial due to a safety issue arise from an incidence of AE or worsened disease, the investigators enter it in the eCRF in accordance with Section 11 "ADVERSE EVENTS."
- If an AE is found at the time of discontinuation, the investigators should perform a follow-up investigation of the AE.
- The investigators should promptly inform the sponsor of the subject's treatment discontinuation.

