14.3 Follow-up Investigation of Subjects with Missing Visits

If a subject miss the follow-up observation as specified in the protocol because the subject failed to visit, the investigators should contact the subject as much as possible to investigate the subject's health condition (confirmation of survival, the presence or absence of an AE). In such a case, enter the contact means, date of contact, subject's condition, and the reason for missing visit in the eCRF. When after trying to contact to the subject, but the subject could not be reached, enter the fact, date of contact, contact means the eCRF.

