15.1.1.2 As-treated analysis set

A subject population consisting of subjects who were enrolled in this clinical trial and implantation of the study device was initiated is defined as as-treated (AT) analysis set. The time when invasion such as incision was made on the access site is regarded as the start of the study procedure. The primary endpoint and secondary safety and efficacy endpoints will be analyzed in the AT analysis set.

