15.1.1.3 Valve implant analysis set

The subject population consisting for all subjects in whom the THV was implanted, and when the subject exited the operation room the implanted THV was maintained is defined as valve implant (VI) analysis set. Subjects for whom the investigational valve was not implanted, including subjects switching to surgery, and TAVI bioprosthetic valve other than the investigational valve was implanted, will not be included in the VI analysis set. As for subjects who received a valve-in-valve procedure, cases with additional investigational valve implantation will be included in the VI analysis set, while cases with additional TAVI bioprosthetic valve other than the investigational valve will be excluded from the VI analysis set. The secondary valve performance endpoints based on the echocardiographic evaluation will be analyzed in the VI analysis set.

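### Subjects left without a study valve appear to count in the primary 1-year mortality test but need not be followed to 1 year, and the supplied text gives no repeat of the test with bailout subjects

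*Combined protocol and SAP*

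**What the plan says.** **Primary set.** Section 15.1.1.2 defines the AT set as enrolled subjects in whom implantation was initiated, with the procedure starting at the first invasion of the access site. It adds: "The primary endpoint and secondary safety and efficacy endpoints will be analyzed in the AT analysis set". No implanted valve is needed. Section 15.1.1.3 deals with "Subjects for whom the investigational valve was not implanted, including subjects switching to surgery" and removes them from the valve implant (VI) set only. Section 4.3 states: "Additional subjects will not be included for discontinued subjects".

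**Follow-up.** For subjects switched to surgery or given another approved transcatheter valve, Section 7.3 says "participation in this trial should be discontinued at the time point, and follow-up observation will not be required thereafter". Section 14.1 lists two relevant grounds for discontinuation: "When the subject is exiting the operation room, the investigational valve has not been implanted" and "The investigational valve was removed". After discontinuation, Section 14.2 asks sites to "also for the safety after discontinuation, perform follow-up investigation as much as possible". The check in Section 14.3 ("confirmation of survival, the presence or absence of an AE") applies to subjects who miss a scheduled visit.

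**Conflicting sentence.** The opening sentence of Section 15.1 limits evaluation to subjects whose valve was expanded at the nominal volume. Read literally, that would drop subjects with no valve.

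**Bailouts.** Enrolment is complete at case review (Section 5.4). Bailout status is assigned at the end of the procedure (Section 7.4). Bailout subjects do not count towards the 30, are outside the analysis set (Section 15.1), and are analysed separately with no test (Section 15.2). They have the same 5-year follow-up as other subjects.

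**The concern.** The plan's only hypothesis test is of death by 1 year. Its analysis set appears to contain subjects for whom the protocol does not require that outcome to be collected. Section 15 gives no rule for unknown status in the binary test, and Kaplan-Meier estimates are to be used only as needed. With about 30 subjects, one death can decide the result, and a subject whose procedure failed is not a random omission.

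Bailout subjects raise a related question. They leave the test after enrolment because of something that happens during the procedure, in an open-label trial. The supplied text assigns no analysis that puts them back. An ITT set of all enrolled subjects is defined in Section 15.1.1.1, but no primary or sensitivity analysis is attached to it.

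**Working it through.** **Inputs.** Performance goal 45%, predicted mortality 20%, one-sided alpha 0.05, 24 evaluable and 30 target subjects (Section 4.3); maximum assumed mortality 26.9% (Section 4.3, rationale for the true value). Conversions to surgery were 1 of 583 in the US trial and 1 of 102 in the European trial of this valve (Section 1.2.2.1). I treat the test as the exact one-sample binomial: d deaths in n pass if P(X ≤ d | n, 0.45) ≤ 0.05, which corresponds to a one-sided 95% exact upper limit below 45%.

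**1. The plan's own figure.** For n=24, P(X ≤ 6)=0.0364 and P(X ≤ 7)=0.0863, so at most 6 deaths pass. Power is P(X ≤ 6 | 24, 0.20)=0.8111, which matches the stated 81.1%. For n=30 the limit is 8 deaths.

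**2. One no-valve subject of unknown status, with 8 deaths among the other 29.**

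| Handling | Deaths/n | p | Upper limit | Result |
|---|---|---|---|---|
| Left out | 8/29 | 0.043 | 44.3% | passes |
| Alive | 8/30 | 0.031 | 43.0% | passes |
| Dead | 9/30 | 0.069 | 46.5% | fails |

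**3. Overall chance.** Let K, the number of no-valve subjects among 30, be binomial with rate 1/583 (expected 30/583=0.051) or 1/102 (expected 30/102=0.294). Assume all of them die, their status is never learned and they are left out. The result changes when the remaining subjects pass alone but fail once the K deaths are added. The low case pairs 1/583 with 20% mortality in the rest; the high case pairs 1/102 with 26.9%.

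| K | Deaths in the rest that change the result | Low: P(K) × P(change) | High: P(K) × P(change) |
|---|---|---|---|
| 1 | exactly 8 of 29 | 0.0490 × 0.101 = 0.50% | 0.2210 × 0.163 = 3.61% |
| 2 | exactly 7 of 28 | 0.0012 × 0.140 = 0.02% | 0.0317 × 0.167 = 0.53% |
| 3 | 6 or 7 of 27 | below 0.01% | 0.0029 × 0.327 = 0.10% |

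The totals are about 0.5% and 4.2%. Pooling the two sources (2/685) gives 0.9% at 20% mortality and 1.4% at 26.9%. Later valve removal is not included, because the documents give no rate for it.

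**4. Adding bailouts to the 30.**

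| Without bailouts | Bailouts added | With bailouts | p | Upper limit | Result |
|---|---|---|---|---|---|
| 8/30, passes | 1, dies | 9/31 | 0.052 | 45.2% | fails |
| 8/30, passes | 2, one dies | 9/32 | 0.039 | 43.9% | passes |
| 9/30, fails | 2, both alive | 9/32 | 0.039 | 43.9% | passes |

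From 7/30, one or two bailouts cannot change a pass even if all die (8/31, p=0.023; 9/32, p=0.039). The documents give no bailout frequency, so no overall chance can be stated.

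**The case against.** **Early deaths are largely covered.** Sections 10.2.9, 11.7 and 14.2 call for follow-up of an adverse event present at discontinuation, and Section 11.7 carries this to recovery or stabilisation, with listed exceptions. Section 11.6 asks for the date of death. The glossary ties switching to surgery to a procedural complication, so a converted subject would ordinarily leave with an ongoing event. The event committee (Section 13.1) reviews reported deaths to 1 year in all enrolled subjects. A reader might infer that treatment-linked deaths after failed procedures would go unseen; these rules do not support that. What stands is narrower. A death after the event has resolved need not be reported, since the glossary ends adverse-event collection at discontinuation, and no rule secures vital status at 1 year.

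**The bailout rule is prespecified and hides nothing.** It confines the claim to nominal-volume use, follow-up is identical, and anyone can compute a combined rate. That is a fair reason to leave the primary rule alone. A reader might infer that the exclusion favours the device; the arithmetic shows it can act in either direction.

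**A separate SAP exists.** Section 15.1.2 refers to one, and it was not supplied. It may contain the repeat or a missing-status rule, so their absence can be asserted only for the text at hand. It would not by itself change the instruction in Section 7.3 that sites follow.

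**The conversion rates are weak proxies.** Both trials excluded dialysis patients, and Section 1.2.2.1 also describes all 583 and all 102 subjects as having received the valve, so a converted subject there may not have lacked one.

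**Conclusion.** The mismatch holds as a minor point and a cheap improvement. On the best reading of Sections 15.1.1.2 to 15.1.2, started subjects with no study valve, or with it later removed, are in the primary set while their required follow-up ends. That reading rests on the AT definition and on their removal from the VI set alone. If the first sentence of Section 15.1 governs instead, they drop out of the test, and the conflict still needs resolving.

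The figure of about 0.5% to 4.2% is a ceiling for the no-valve case: it assumes that every such subject dies, that status is never learned, and that the borrowed rates apply. Zero or one such subject is likely. Nothing here shows an error in the sample size or the 81.1% power. For bailouts, the documents support a request for a sensitivity analysis, not a finding of bias.

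**What to change.** (a) Amend Sections 7.3, 14.1/14.2 and 15.1 so that every non-bailout subject whose procedure was started stays in the AT primary set, whether or not a study valve was implanted or later removed. Vital status at day 365 should be obtained for each unless consent to contact is withdrawn. Enrolment to this set is closed (Section 27), so the contact may have to be retrospective.

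(b) Keep the primary rule and the bailout definition unchanged. Repeat the primary exact test in all started subjects, bailouts included, as a sensitivity analysis.

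The Synopsis and Section 7.4 word the bailout condition slightly differently. It is tempting to settle this by calling any non-nominal inflation a bailout. That would drop the medical-reason condition and widen a post-enrolment exclusion, so it should not be done.

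Cost: one vital-status contact for probably zero or one subject, one extra exact test on bailout data already being collected, and a few wording changes. Enrolment, sample size, alpha and the decision rule are untouched.

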7.4 Bailout Treatment Registry

Patients in whom deployment of the THV by balloon dilatation at a nominal volume was impossible for a medical reason will be regarded as bailout cases, and these cases will be included in the bailout treatment registry at the end of study procedure. The bailout cases will be enrolled separately from the target sample size of this trial (30 subjects), and will not be included in the analysis set for the safety and efficacy evaluation of EWJ-003. The same post-procedural follow-up observation will be performed as that for subjects with successful valve implant procedure at a nominal volume, and the follow-up observation will be performed for up to 5 years post-procedure.

In the continued access registry, irrespective of whether the THV was implanted at a nominal volume or not, subjects who received the study procedure will be included in this registry.

- 65 -

[figure not shown]

Figure 7-1: Bailout treatment registry treatment flow

- 66 -

8 CONCOMITANT THERAPY

8.1 Anticoagulation/Antiplatelet Therapy

As a general rule, the principal investigator or subinvestigators should provide anticoagulation/antiplatelet regimen in accordance with Table 8-1. However, considering individual subject's clinical circumstance including validity of contraindications for a subject, the dosage, concomitant drugs, timing of administration, and duration of administration should be decided, at the discretion of the primary physician. For example, if a subject with atrial fibrillation receives warfarin potassium, or a subject with obstructive arteriosclerosis or a subject with a stent implanted in the peripheral blood vessel or coronary artery (including bypass graft) is on an antiplatelet agent other than aspirin, taking continuous use into consideration, anticoagulation/antiplatelet therapy should be provided. Therefore, when anticoagulation/antiplatelet therapy different from those recommended in Table 8-1 (e.g., ticlopidine hydrochloride and clopidogrel sulfate) is given, the protocol deviation is not applicable.

Chronic dialysis patients, compared with non-dialysis patients, have a strong bleeding tendency, often leading to difficulty in hemostasis, patients on antiplatelet drugs and/or anticoagulant (excluding anticoagulant at dialysis) before the procedure, these drugs should be discontinued at least 14 days before the procedure as a general rule, so that the effect of these drugs fades away.

Table 8-1: Recommended anticoagulation/antiplatelet regimen

Drug	Pre-procedure	At procedure	Post-procedure
Heparin	None	5000 IU/dose, then heparin will be given to achieve and maintain ACT ≥ 250 sec as needed	None
Aspirin	None	None	75 - 100 mg/day, once daily continued indefinitely

[Pre-procedural antiplatelet therapy]

Considering bleeding risk, pre-procedural anticoagulation/antiplatelet therapy will not be given. However, if a platelet function inhibitory action is required, aspirin, etc. should be carefully administered in accordance with the package insert.

[Anticoagulant therapy at procedure]

After intravenous administration of heparin 5000 IU/dose, heparin will be given to achieve and maintain activated clotting time (ACT) ≥ 250 seconds as needed throughout the course of the procedure. Monitor the ACT at regular intervals, and record it in the source document.

[Post-procedural antiplatelet therapy]

After the procedure, aspirin monotherapy will be given at a dose of 75 to 100 mg/day for an indefinite period after study procedure.

- 67 -

<Rationales for the setting>

Considering bleeding risk related to the procedure, irrespective of the implantation approach, pre-procedural antiplatelet therapy will not be given. For the anticoagulant therapy during procedure, in addition to thromboprophylaxis, in order to inhibit enhancement of the blood coagulation system induced by damage on the vascular inner wall and prevent consumption of the blood coagulation factor, heparin will be administered. As for post-procedural antiplatelet therapy, compared with non-dialysis patients, dialysis patients have a higher trend toward bleeding, and therefore similarly to the antiplatelet therapy given in the advanced medical care at Osaka University Hospital, administration of aspirin single-agent for indefinite period was recommended. Aspirin is an agent that undergoes hepatic metabolism, and therefore the pharmacokinetics of these antiplatelet drugs is not affected in dialysis patients with impaired renal excretion.

8.2 Prophylactic Administration of Antibiotics

An antibiotic agent will be administered to the subjects who undergo implantation procedure of the study device immediately before the start of the procedure. Regardless of the type of antibiotic agent, considering the use status of antibiotic agents at each study site, possible drug-resistant bacteria, and an impact on subject's renal function, antibiotic agents should be chosen. If methicillin-resistance is suspected, consider the use of vancomycin.

<Rationales for the setting>

In the subjects receiving implantation of the study device, incidence of endocarditis associated with infection may be fatal and therefore the subjects should be prophylactically treated for infections per the recommendations by the AHA^[54] prior to the procedure.

8.3 Precautions for Concomitant Drugs

The following concomitant drugs should be carefully used, and the concomitant use should be avoided as much as possible. When the concomitant use is necessary, concomitant use other than single use should be avoided.

- Non-steroidal anti-inflammatory drug (indomethacin, etc.)
- Steroids, tacrolimus preparations, and other immunosuppressants

<Rationales for the setting>

Since non-steroidal anti-inflammatory drugs may cause interactions with aspirin (enhancing), concomitant use other than single use in necessary cases should be avoided. Since steroids, tacrolimus preparations, and other immunosuppressants may affect the immune system, concomitant use other than single use in

the procedure (counting the procedure day as Day 0) throughout the observation period, and for antibiotics from 7 days prior to the procedure day (counting the procedure day as Day 0) to hospital discharge (or 7 days post-procedure, whichever earlier). The name, duration of treatment, reasons for treatment, route of administration, and dosage of the used anticoagulants/antiplatelet drugs and antibiotics should be entered in eCRF. However, the data on antibiotics will not be collected for the continued access registry.

8.6.2 Blood purification

Concerning periprocedural blood purification therapy, for dialysis given from immediately before the study procedure through to post-procedure hospital discharge (day of discharge or 7 days post-procedure, whichever earlier), the date of therapy, type of dialysis, dialysis condition, and anticoagulant used at dialysis should be entered in eCRF. Also at 1 year post-procedure, similarly to the periprocedural period, dialysis data should be collected to check the dialysis status.

8.6.3 Other concomitant drug/therapy

After the start of study procedure, the data on other drugs and therapies concomitantly used in the treatment of an AE and complication that can be a risk factor will be collected until 1 year post-procedure. Of the concomitant drugs, only for the cardiovascular agents applicable to the following therapeutic category, the name, duration of administration, reason for use, route of administration, and dosage should be entered in eCRFs, and for the concomitant therapies, the name, duration of concomitant use, and reason for concomitant use should be entered in eCRFs. However, for Continued Access Registry, these data may be collected as much as possible.

<Concomitant cardiovascular drugs for which data will be collected>

- Inotropic agent
- Antiarrhythmic agent
- Diuretic
- Hypotensive agent
 - Angiotensin-converting enzyme inhibitor (ACE-I)
 - Angiotensin II receptor blocker (ARB)
 - Renin inhibitor
 - β -blocker
 - α -blocker
 - α - β -blocker
 - Calcium-channel blocker (CCB)
 - Aldosterone receptor antagonist
- Capillary stabilizer

necessary cases should be avoided.

8.4 Periprocedural Hemodialysis

Perform periprocedural hemodialysis in accordance with the following recommendations:

[Pre-procedural hemodialysis]

- For hemodialysis patients, perform hemodialysis until achievement of this dry weight on the day before study procedure as a general rule.
Do not change the anticoagulant therapy.
- For peritoneal dialysis patients, continue peritoneal dialysis as usual until the day before study procedure.

[Post-procedural hemodialysis]

- Considering post-procedural hemodynamics, resume dialysis at the discretion of the investigator.
- In case of the hemodialysis, it is recommended to use anticoagulant with shorter half-life (e.g. nafamostat mesilate) to reduce bleeding risk.
- Do not change dialysis conditions until 1 year post-procedure as a general rule. However, the dialysis conditions may be changed if it is based on the medical judgement.

